6.2.9. Duration of Each Targeted COVID-19 Sign/symptom

Duration of each targeted COVID-19 signs/symptoms is defined as (First Date when the symptom alleviated/resolved) – (First Dose Date) +1 for each participant with baseline severity of mild, moderate, or severe.

For duration of each targeted COVID-19 sign/symptom, a Kaplan-Meier analysis providing the median and quartiles will be provided for each treatment group for mITT1 population set. Two additional figures (Number of Participants and Median Time to Sustained Alleviation of Each Targeted Sign/Symptom by Treatment Group [mITT1]) will be included for the endpoint of Duration of Each Targeted COVID-19 Sign/Symptom.

6.2.10. Progression to a Worsening Status in 1 or More Self-reported COVID-19 Associated Symptoms through Day 28

Participants will record a daily severity rating of their symptom severity over the past 24 hours based on a 4-point scale in which 0 is reported if no symptoms were present; 1 if mild; 2 if moderate; and 3 if severe.

Vomiting and diarrhea will each be rated on a 4-point frequency scale where 0 is reported for no occurrence, 1 (mild) for 1 to 2 times, 2 (moderate) for 3 to 4 times, and 3 (severe) for 5 or greater.

Progression to a worsening status for any targeted symptom will be derived programmatically based upon increasing severity (ie, the first time any targeted symptom worsens after treatment relative to baseline):

Progression to worsening (Yes/No)	
Increasing severity	Yes
Not increasing severity	No

The proportion of participants with progression (increasing severity for any targeted symptom) will be summarized by treatment group. Treatment comparison between groups will be presented as odds ratios with 95% CIs and p-value based on logistic regression model. The analyses will be done using mITT1 population. Missing severity at baseline will be treated as mild.

The above definition of worsening was derived only from participant diary data, to align the worsening with the primary and keys secondary endpoint, an expanded evaluation of

worsening will be assessed to include hospitalization due to COVID-19 and death of any cause. An expanded definition of worsening of signs and symptoms that will include CRF data (hospitalization due to COVID-19 and death of any cause) is defined as follows: Participant with hospitalization due COVID-19 or death of any cause will be considered as having worse signs and symptoms, this definition overrides the observed worsening of signs and symptoms from participant diary data. To incorporate hospitalization and death in the expanded worsening of signs and symptoms, date of hospitalization and date of discharge will be used.

To evaluate the progression to worsening of symptoms attributed to COVID-19, the following analysis will be performed for both worsening and expanded worsening and treatment comparison between groups will be done using the same statistical method as mentioned above:

- Proportion of participants with any progression to worsening of targeted symptoms attributed to COVID-19 Day 2 to Day 6 (during treatment).
- Proportion of participants with any progression to worsening of targeted symptoms attributed to COVID-19 Day 7 to Day 28 (post treatment).

6.2.11. Proportion of Participants with a Resting Peripheral Oxygen Saturation $\geq 95\%$ at Days 1 and 5

The oxygen saturation level will be measured for each participant. A resting peripheral oxygen saturation will be derived programmatically based on following table:

Oxygen saturation (Yes/No)	
$\geq 95\%$	Yes
$< 95\%$	No

The count and proportion of participants with a resting peripheral oxygen saturation $\geq 95\%$ will be summarized by treatment group and by visits (Days 1 and 5). A cross tabulation will be presented for both Day 1 and Day 5, ie, for each proportion presented at Day 1, both proportions at Day 5 will be summarized. Treatment comparison between group for the odds ratio (baseline (Day 1) $\geq 95\%$ vs $< 95\%$) of comparing oxygen saturation $\geq 95\%$ at Day 5 will be analyzed with a Breslow-Day test for homogeneity of the odds ratios. The analyses will be done using mITT1 populations. Missing data at Day 1 or Day 5 will be excluded from the analysis.

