
 To compare PF-07321332/ritonavir versus placebo for COVID-19-related medical visits in nonhospitalized adult participants with COVID-19 who are at low risk of progression to severe disease. 	
 Number of COVID-19-related medical visits through Day 28. 	
 The difference in the estimated rate of the number of COVID-19-related medical visits through Day 28 in nonhospitalized adult patients with COVID-19 who are at low risk of progression to severe disease and were treated ≤ 5 days after COVID-19 symptom onset.

Objectives	Endpoints	Estimands
	
 Number of days in hospital and ICU stay in participants with COVID-19-related hospitalization through Day 28. 	
This will be estimated without regard to adherence to randomized treatment.
 
 The difference in the estimated rate of number of days in hospital and ICU stay in patients with COVID-19-related hospitalization through Day 28 in nonhospitalized adult patients with COVID-19 who are at low risk of progression to severe disease and were treated ≤ 5 days after COVID-19 symptom onset. This will be estimated without regard to adherence to randomized treatment.

 To compare PF-07321332/ritonavir to placebo for the duration and severity of signs and symptoms in nonhospitalized symptomatic adult participants with COVID-19 who are at low risk of progression to severe disease. 	
 Proportion of participants with severe signs/symptoms attributed to COVID-19 through Day 28. Time (days) to sustained resolution of all targeted COVID-19 signs/symptom through Day 28. Duration of each targeted COVID-19 sign/symptom. Progression to a worsening status in 1 or more self-reported COVID-19-associated symptoms through Day 28. Proportion of participants with a resting peripheral oxygen saturation $\geq 95\%$ at Days 1 and 5. 	
 Not Applicable.

 To determine the PK of PF-07321332 in nonhospitalized adult participants with COVID-19 who are at low risk of progression to severe disease. 	
 PF-07321332 PK in plasma and whole blood (if feasible). 	
 Not Applicable.

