6. ANALYSES AND SUMMARIES

6.1. Primary Endpoint

6.1.1. Primary Endpoint/Estimand Analysis

6.1.1.1. Main Analysis

The primary endpoint is time (days) to sustained alleviation of all targeted COVID-19 signs/symptoms through Day 28 in the mITT1 population.

Sustained alleviation of all targeted COVID-19 signs/symptoms is defined as the event occurring on the first of 4 consecutive days when all symptoms scored as moderate or severe at study entry are scored as mild or absent AND all symptoms scored mild or absent at study entry are scored as absent. The first day of the 4 consecutive-day period will be considered the First Event Date.

For symptoms with no reported severity in baseline, the symptom will have to be absent in order to be counted as sustained alleviated/resolved (missing severity at baseline will be treated as mild).

Day 25 is the last possible day the symptom alleviation and resolution endpoints can be achieved (definition includes data from the subsequent three days) and Day 28 is the last day participants report their daily signs and symptoms.

The time to sustained symptom alleviation/resolution for the purpose of this study is defined as:

- For a participant with sustained symptom alleviation/resolution (event), time to event will be calculated as (First Event Date) – (First Dose Date) +1.

- For a participant that either completes Day 28 of the study or discontinues from the study before Day 28 without sustained symptom alleviation/resolution (censored), censoring date will be at the last date on which symptom alleviation/resolution is assessed, and time will be calculated as (Censoring Date) – (First Dose Date) +1 or Day 25 whichever occurs first.

The decision to require 4 consecutive days of all targeted symptoms alleviation/resolution was based on exploratory analyses of data from the ACTIV-2/A5401 study, which suggested that this choice (rather than requiring fewer consecutive days) better captured sustained symptom resolution with low probability of subsequent relapse.

Participants who are hospitalized for the treatment of COVID-19 or death from any cause during the 28-day period will be classified as not achieving sustained symptom alleviation and will be censored at Day 25.

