Proportion of participants with any severe targeted signs/symptoms attributed to COVID 19 at Day 1(baseline).	Supplemental analysis for secondary endpoint	mITT1	Any severe (ie, any targeted symptoms with severe baseline score) LOCF for missing data.	Logistic regression model
Proportion of participants with any severe targeted signs/symptoms	Supplemental analysis for secondary endpoint	mITT1	Any severe (ie, any targeted symptoms with severe baseline score) LOCF for missing data.	Logistic regression model

Endpoint	Analysis Type	Population	Data Inclusion and Rules for Handling Intercurrent Events and Missing Data	Analysis Model
attributed to COVID 19 from Day 2 to Day 6 (during treatment)				
Proportion of participants with any severe targeted signs/symptoms attributed to COVID 19 from Day 7 to Day 28 (post treatment)	Supplemental analysis for secondary endpoint	mITT1	Any severe (ie, any targeted symptoms with severe baseline score) LOCF for missing data.	Logistic regression model
Proportion of participants with severe signs/symptoms attributed to COVID 19 through Day 28.	Supplemental analysis for secondary endpoint	mITT1	Observed proportions for each targeted signs and symptom with severe category only will be plotted over time through Day 28. Additionally, observed proportion of participants reporting the presence of each targeted sign and symptom that is mild, moderate or severe categories will also be presented	Plot/Figure
Time (days) to sustained resolution of all targeted COVID-19 signs/symptom through Day 28.	Secondary analysis	mITT1	All data collected will be included. Missing severity at baseline will be treated as mild. Other missing data will be estimated with KM (lifetest) procedure	Kaplan-Meier & Log rank test
Duration of each targeted COVID-19 sign/symptom.	Secondary analysis	mITT1	All data collected will be included regardless of intercurrent events. Missing data will not be imputed.	Kaplan-Meier estimate, Descriptive statistics (median, quartiles)
Progression to a worsening status in 1 or more self-reported COVID19 associated symptoms through Day 28.	Secondary analysis	mITT1	All data collected will be included regardless of intercurrent events. Missing severity at baseline will be treated as mild.	Logistic regression model

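### SAP 6.2.9 ends symptom duration at the first alleviated or resolved date with no consecutive-day rule, at odds with its own figures of sustained alleviation

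*SAP*

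**What the plan says.** Protocol section 3 has an objective of comparing the arms "for the duration and severity of signs and symptoms", and the duration of each targeted symptom is one of its secondary endpoints. Protocol 9.3.3 leaves the definition of this endpoint to the SAP.

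SAP 6.2.9 says that duration "is defined as (First Date when the symptom alleviated/resolved", less the first dose date, plus 1, for participants whose baseline severity was mild, moderate or severe. For the analysis, "a Kaplan-Meier analysis providing the median and quartiles will be provided for each treatment group for mITT1 population set". The Appendix 1 entry is "Kaplan-Meier estimate, Descriptive statistics (median, quartiles". The same paragraph of 6.2.9 adds figures for this endpoint showing "Median Time to Sustained Alleviation of Each Targeted Sign/Symptom by Treatment Group".

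The related endpoints state a persistence rule. In SAP 6.1.1.1, sustained alleviation "is defined as the event occurring on the first of 4 consecutive days when all symptoms scored as moderate or severe at study entry" have fallen to mild or absent and all other symptoms are absent. SAP 6.2.8 requires every targeted symptom to be absent for 4 days running. SAP 6.1.1.1 justifies 4 days from exploratory analyses of another study, saying that this choice, compared with fewer days, "better captured sustained symptom resolution with low probability of subsequent relapse".

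**The concern.** A programmer who follows the 6.2.9 formula would stop the clock on the first diary day that qualifies. A programmer who follows the figure titles would wait for a sustained run. Both would be reporting the same endpoint.

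The paired term alleviated/resolved leaves a second choice open. For a symptom that was mild at baseline the two words coincide, since both mean absent. For one that was moderate or severe, alleviation is reached while the symptom is still present and mild, and resolution is not. One day or 4 days, crossed with alleviated or resolved, gives four possible endpoints.

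Censoring is also unstated. SAP 6.2.8 borrows the primary endpoint's censoring for sustained resolution; 6.2.9 does not. Appendix 1 says only that all data are used and missing data are not imputed.

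At stake is whether the per-symptom durations describe the end of a symptom or merely its first good day, and whether table and figures in the study report agree.

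**Working it through.** The plan gives no expected duration, relapse rate or power for this endpoint, so there is no figure to reproduce. The check has two parts.

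**1. Ordering (no assumptions about rates).** Absent also satisfies the alleviation criterion, so the first date on which a symptom is alleviated or resolved is the first alleviated date. The first day of a 4-day alleviated run is itself an alleviated day. Hence, for every participant, first alleviated day ≤ first day of a 4-day run. Literal durations are equal or shorter, never longer.

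A hypothetical example, with first dose on Day 1: a mild cough is absent on Day 3, present on Days 4 to 15, and absent from Day 16.
- Literal rule: 3 − 1 + 1 = 3 days.
- 4-day rule: 16 − 1 + 1 = 16 days.

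**2. Size (assumed rates).** Each symptom follows a two-state daily chain: present on Day 1, clearing with probability c per day, returning with probability r per day once clear. There are 28 diary days and 200,000 simulated participants per arm. Assumed values are c = 0.12 for placebo, c = 0.16 (or 0.12) for active, and r from 0 to 0.20. None of these comes from the documents.

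The single-day medians can be confirmed by hand. The chance of a first clear day by Day d is 1 − (1 − c)^(d−1).
- Placebo: 1 − 0.88^5 = 0.472 by Day 6 and 1 − 0.88^6 = 0.536 by Day 7. The interpolated median is 6 + (0.500 − 0.472)/(0.536 − 0.472) ≈ 6.4.
- Active: 1 − 0.84^3 = 0.407 by Day 4 and 1 − 0.84^4 = 0.502 by Day 5. The interpolated median is 4 + (0.500 − 0.407)/(0.502 − 0.407) ≈ 5.0.

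Medians in days, placebo / active (difference, placebo minus active):

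| Assumed scenario | Single-day rule | 4-day rule |
|---|---|---|
| Faster clearing on active, no relapse | 6.4 / 5.0 (1.5) | 6.4 / 5.0 (1.5) |
| Faster clearing, relapse 0.10 in both arms | 6.4 / 5.0 (1.5) | 9.0 / 7.0 (2.0) |
| Faster clearing, relapse 0.20 in both arms | 6.4 / 5.0 (1.5) | 13.0 / 10.2 (2.8) |
| Same clearing, relapse 0.20 v 0.10 | 6.4 / 6.5 (−0.1) | 13.0 / 9.0 (4.0) |
| Faster clearing, relapse 0.20 v 0.10 | 6.4 / 5.0 (1.5) | 13.2 / 7.0 (6.1) |
| Faster clearing, relapse 0.10 v 0.15 | 6.4 / 5.0 (1.5) | 9.0 / 8.4 (0.6) |
| Faster clearing, relapse 0.10 v 0.20 | 6.4 / 5.0 (1.4) | 9.0 / 10.3 (−1.3) |

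Differences were taken before rounding. The −0.1 is simulation noise around zero.

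Three things follow.
- The single-day column depends only on clearing. It cannot register relapse, in either arm.
- The share of placebo participants whose duration is shorter under the single-day rule is 27% at relapse 0.10 and 48% at relapse 0.20. It is 1% with no relapse, from symptoms that clear too late to complete a 4-day run by Day 28.
- The arm difference under the single-day rule can be smaller than, equal to or larger than under the 4-day rule, or of opposite sign.

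**The case against.** The best defence is that a sustained rule was meant all along. The figures for this very endpoint are of sustained alleviation, and the formula has the same shape as the primary endpoint's, where the event date is day one of a 4-day run. That is a plausible account of intent. But 6.2.9 neither uses the defined event date nor mentions 4 days, and Appendix 1 does not supply them. If a sustained rule was intended, the formula is incomplete; if not, it contradicts the figures. It needs correcting either way, although a single-day rule should not be described as the sponsor's settled choice.

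Three stronger readings are tempting, and the documents do not support them.

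- *The literal rule shrinks the difference between arms.* That needs fluctuation to be similar in both arms, and no per-symptom relapse data are given for either. Even with equal relapse, the ratio of medians hardly moves (0.77 against 0.78 to 0.79). The difference in mean time restricted to Day 25 moves little too (1.78 against 1.90 days at relapse 0.10; 1.80 against 1.83 at 0.20).
- *The SAP concedes that shorter runs relapse for each symptom.* Its rationale is comparative, unquantified, drawn from another study, and concerns all targeted symptoms together.
- *No sustained per-symptom result would be reported.* The planned figures would show one.

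It also stands that little rests on the endpoint. It is summarised by arm with no test, hazard ratio or confidence interval for a difference, it is not on the Hochberg list in SAP 5.1, and SAP section 2 makes all further p-values nominal.

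**Conclusion.** The point holds as a defect of definition. As written, the formula lets one good day end a symptom, leaves alleviated or resolved open, and disagrees with the figures planned for the same endpoint. That literal durations are equal or shorter follows from logic alone. How much shorter depends on relapse: in the assumed scenarios the placebo median is understated by 0, 2.6 (9.0 − 6.4) or 6.6 (13.0 − 6.4) days at daily relapse of 0, 0.10 and 0.20. These are illustrations, not estimates for this trial. The effect on the comparison between arms is of unknown direction. Impact is limited because the endpoint is descriptive, but it serves a stated objective and the correction is cheap, so it should be made.

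**What to change.** In SAP 6.2.9, for each symptom present at baseline, define the end date as the first of 4 consecutive days on which that symptom meets the primary endpoint's alleviation criterion: moderate or severe at entry falling to mild or absent, mild at entry falling to absent. This matches the planned figures. Duration is then that date minus the first dose date, plus 1.

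State the primary endpoint's censoring: participants without the event at their last assessed date or Day 25, whichever is earlier, and those hospitalised for COVID-19 or who die within the 28 days at Day 25.

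If per-symptom sustained resolution (absent for 4 consecutive days) is also wanted, report it separately under that name. Use one definition in the table, the figures and Appendix 1.

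The cost is SAP wording and reuse of the existing 4-day algorithm, symptom by symptom, on diary data already collected. The downside is longer reported durations and more participants censored at Day 25, so some upper quartiles may not be estimable.

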9.3.1. General Considerations

Descriptive statistics for all efficacy endpoints by treatment group and visit will be provided.

The number of participants screened will be reported. The number of participants randomized to the double-blind treatment phase, completing the study drug administration, completing the study, and discontinued the study will be summarized from the FAS analysis set for each treatment group.

Baseline demographic and other characteristics will be tabulated for the FAS analysis set and summarized by treatment group. Quantitative variables will be described by standard descriptive statistics (mean, standard deviation, minimum, and maximum), and qualitative variables will be summarized by frequency tables with number and proportion in each category (with the corresponding sample sizes).

For continuous endpoints, MMRM analysis of covariance model will be used to analyze change from baseline over time. Estimated mean differences between treatments and their respective 95% CI and p-values will be calculated.

Binary endpoints will be summarized with the number and percent of participants satisfying the endpoint. Comparisons between groups will be presented as odds ratios with 95% confidence intervals based on logistic regression analysis with terms for treatment.

For categorical endpoints, proportion of participant for each category will be summarized for each group.

For count endpoints, the total number of the events and average number of events will be summarized for each group.

Time-to-event endpoints will be summarized with Kaplan-Meier curves. Log-rank test will be used to compare the median time-to-event between the treatment group. Rate ratios or hazard ratios and the associated 95% 2-sided CIs will be estimated by Cox proportional hazards models, including treatment and the strata as covariate.

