2.1. Study Objectives, Endpoints, and Estimands

Primary Efficacy Objective:

To compare the efficacy of PF-07321332/ritonavir to placebo for the treatment of symptomatic COVID-19 in nonhospitalized adult participants with COVID-19 who are at low risk of progression to severe disease.

Secondary Efficacy Objective:

To compare PF-07321332/ritonavir versus placebo for COVID-19-related hospitalization and all-cause mortality in nonhospitalized adult participants with COVID-19 who are at low risk of progression to severe disease.

To compare PF-07321332/ritonavir versus placebo for COVID-19-related medical visits in nonhospitalized adult participants with COVID-19 who are at low risk of progression to severe disease

To compare PF-07321332/ritonavir to placebo for the duration and severity of signs and symptoms in nonhospitalized symptomatic adult participants with COVID-19 who are at low risk of progression to severe disease.

Secondary Safety Objective:

To describe the safety and tolerability of PF-07321332/ritonavir relative to placebo in the treatment of nonhospitalized symptomatic adult participants with COVID-19 who are at low risk of progression to severe disease.

Other Secondary Objectives:

To determine the PK of PF-07321332 in nonhospitalized adult participants with COVID-19 who are at low risk of progression to severe disease.

To describe the viral load in nasal samples over time in nonhospitalized adult participants with COVID-19 who are at low risk of progression to severe disease.

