5.2.5. Analyses for Time-to-Event Endpoints

Time-to-event endpoints (ie, Time (days) to sustained resolution of all targeted signs/symptoms through Day 28) will be summarized with Kaplan-Meier curves. Log-rank test will be used to compare the time-to-event between the treatment group.

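### Each targeted symptom's duration is summarised by arm only, with no between-arm estimate or confidence interval, although the objective is to compare the arms

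*SAP*

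**What the plan says.** The objective, in SAP 2.1 and Protocol section 3, is "To compare PF-07321332/ritonavir to placebo for the duration and severity of signs and symptoms". Duration of each targeted sign or symptom is one of the endpoints listed under it in the protocol.

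Protocol 9.3.1 gives the general rule for time-to-event endpoints: Kaplan-Meier curves, then "Log-rank test will be used to compare the median time-to-event between the treatment group", and "Rate ratios or hazard ratios and the associated 95% 2-sided CIs will be estimated by Cox proportional hazards models", with treatment and strata in the model.

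For this endpoint, SAP 6.2.9 plans "a Kaplan-Meier analysis providing the median and quartiles will be provided for each treatment group" in mITT1, plus two figures by treatment group (numbers of participants and median times). The Appendix 1 row reads "Kaplan-Meier estimate, Descriptive statistics (median, quartiles". Neither place names a test, an effect estimate or an interval for a difference.

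The SAP's general rule in 5.2.5 opens "Time-to-event endpoints (ie, Time (days) to sustained resolution of all targeted signs/symptoms through Day 28) will be summarized with Kaplan-Meier curves" and goes on "Log-rank test will be used to compare the time-to-event between the treatment group". Its bracket names sustained resolution only, and it mentions no hazard ratio.

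SAP Appendix 4 marks 11 symptoms as targeted for analysis.

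**The concern.** The planned output is 11 pairs of medians and quartiles, to be read against a comparative objective. SAP 6.2.9 computes duration as a date difference plus one, so values are whole days and a median moves in one-day steps. A reader who sees 6 days in one arm and 7 in the other has nothing that shows whether the gap is within chance. Equal medians are equally uninformative about how large an effect could have been missed.

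Other endpoints under the same objective do get a between-arm analysis. Severity (6.2.7) and worsening (6.2.10) have odds ratios with 95% CIs and p-values, and sustained resolution (6.2.8) has a log-rank test. The SAP gives no reason for treating duration differently.

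**Working it through.** **1. The plan's own figure.** The documents give no size calculation for symptom duration. The nearest figure is the primary endpoint's: medians of 6 and 8 days, two-sided alpha 0.05, 90% power, about 515 events. With exponential times the hazard ratio is 6/8 = 0.75. Freedman's formula gives (1.960 + 1.282)² × ((1 + 0.75)/(1 − 0.75))² = 10.51 × 49 = 515, so it reproduces. Schoenfeld's gives 508.

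**2. Inputs for single symptoms.**
- From the documents: about 1880 participants at 1:1, so 940 per arm; only those with the symptom at baseline enter (SAP 6.2.9); Day 25 as the last event day (SAP 6.1.1.1, for alleviation and resolution; applied here to duration).
- Assumed, because the documents do not give them: exponential durations, true medians and symptom prevalence. Prevalence of 10% to 80% gives 94 to 752 per arm.

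**3. Chance that two whole-day medians differ with no drug effect.** Let n be the number per arm and m the true median. With times rounded up to whole days, F(d) = 1 − 2^(−d/m). The sample median is at most d when at least n/2 participants have a time of at most d, which is a binomial tail with probability F(d). The chance of a gap of one day or more is 1 − Σ P(median = d)².

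- *m = 5.5, n = 650.* F(5) = 0.468 and F(6) = 0.531. P(median ≤ 5) = 0.053 and P(median ≤ 6) = 0.945, so P(median = 6) = 0.892. Chance of a gap: 1 − (0.892² + 0.053² + 0.055²) = 20%. A simulation of 4,000 trials gave 21%.
- *m = 9, n = 280.* The medians 8, 9, 10 and 11 have probabilities 0.097, 0.424, 0.380 and 0.089. Chance of a gap: 1 − 0.342 = 66%.
- *Whole-number m, large n.* The true median sits on a rounding step, each arm is close to a coin flip between adjacent days, and the chance is about 50%.

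For medians of 5 to 9 days and 280 to 650 per arm, the range is therefore about 20% to 66%. On a wider grid (medians 4, 5.5, 6, 6.5, 7, 7.5, 8 and 10 days; 94 to 752 per arm; 10,000 runs each) it was about 16% to 81%. For example, at a 7.5-day median it was 75%, 53% and 35% at 10%, 40% and 80% prevalence. Points between grid values can fall lower: a 4.5-day median with 650 per arm gives about 10%. A gap of two days or more occurred in 0% to 47% on that grid.

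**4. What a hazard ratio would add.** Expected events are 2n(1 − 2^(−25/m)). The 95% CI is the hazard ratio divided and multiplied by exp(1.96 × 2/√events).

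| Case | Events | CI factor |
|---|---|---|
| m = 10, 10% prevalence | 155 | 1.37 |
| m = 7, 40% prevalence | 689 | 1.16 |
| m = 4, 80% prevalence | 1484 | 1.11 |

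Power for a true shortening from 7 to 6 days (hazard ratio 6/7) is about 0.17, 0.53 and 0.82 at 10%, 40% and 80% prevalence. The interval would show which symptoms carry useful information and which do not.

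**5. Multiplicity.** Eleven independent unadjusted intervals under no effect: 1 − 0.95¹¹ = 43% chance that at least one excludes 1.

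**The case against.** **The protocol permits this.** Protocol 9.3.1 is a general section. Protocol 9.3.3 lists symptom duration among the endpoints whose definition and analysis are left to the SAP, and section 9 lets the SAP modify the protocol where appropriate. A reader might infer that the SAP breaches the protocol. It does not. What stands is that the delegated analysis does not match the comparative objective, and no reason is given.

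**SAP 5.2.5 may already cover duration.** Its bracket also leaves out the primary endpoint, which gets a log-rank test in 6.1.1.1, so the list is not reliably complete. That is a fair reading. It would add a p-value, but no effect size or interval, and the Appendix 1 row still lists no test.

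**The objective is served elsewhere.** A reader might infer that the objective goes unanswered. That is too strong: sustained resolution, severity and worsening all compare the arms under it. Single-symptom duration is a supportive breakdown with no estimand, and it is not in the Hochberg list in SAP 5.1.

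**Quartiles are planned too.** With a true hazard ratio of 1.20, medians of 5 to 9 days and 280 to 650 per arm, the 25th, 50th and 75th percentiles all coincide in only about 4% of comparisons or fewer. The planned output would therefore rarely hide such a shift altogether. Quartiles still carry no measure of uncertainty for a difference.

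**No alpha remains, so description is defensible.** SAP section 2 says all further analyses use nominal p-values. The 43% figure is a real cost of adding intervals. But the protocol and SAP respond to the lost alpha by reporting leading secondary endpoints as a point estimate with a 95% CI, which is what is asked for here.

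**Conclusion.** The point holds as a cheap improvement to a supportive endpoint. As written, symptom durations have no between-arm estimate, no interval and no clearly assigned test, while the objective is to compare.

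Chance one-day gaps between medians are common: about 20% to 66% of comparisons under the narrower assumptions, and about 16% to 81% on the wider grid. The result depends strongly on where the true median lies relative to a whole day, and it rests on assumed exponential durations, prevalences and medians.

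A reader might want to turn these rates into an expected number of the 11 symptoms. The documents do not support that, because they give no prevalence or median for any symptom and the 11 need not share one. A reader might also infer that sustained resolution has no hazard ratio. SAP 6.2.8 says its analysis will resemble the primary endpoint's, and 6.1.1.2 gives that endpoint a Cox model, so the most that can be said is that 5.2.5 and Appendix 1 do not confirm it.

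**What to change.** In SAP 6.2.9 and its Appendix 1 row, add for each targeted symptom a Cox hazard ratio with 95% CI, with treatment and the randomisation strata (region, vaccination status, symptom onset) in the model, in mITT1 participants who had that symptom at baseline. Show the 11 results in one forest plot beside the medians, labelled nominal and not adjusted for multiplicity.

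For sustained resolution, only confirm in 5.2.5 and Appendix 1 that following the primary analysis, as 6.2.8 says, includes the Cox hazard ratio.

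The cost is a sentence in the SAP and one figure. The Kaplan-Meier estimates already need the same event and censoring dates, so no new data or derivation is required. The downside is 11 more unadjusted intervals, with about a 43% chance that at least one excludes 1 under no effect if they were independent; hence the label.
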